9.0 Study Timelines*

Phase 2: Individual participants are in the study for three months (Baseline, 1-month at-home survey, 3-month follow-up).

Phase 3: Individual participants are in the study for nine months (Baseline, 1-month, 3-month, 6-month follow-ups).

All study subjects will be enrolled over the course of 60 months.

10.0 Subject Population*

Inclusion Criteria:

YMSM couples who express interest in We Test must demonstrate the following inclusion criteria to be enrolled in the study:

- At least one partner must be HIV-negative or status unknown
- THE INDEX PARTNER must be 15-24 years old
- YMSM under age 18 MUST HAVE AN AGE CONCORDANT PARTNER TO PARTICIPATE IN THIS STUDY, I.E., MINORS may only participate in the study with a partner within 2 years of age OF THE MINOR SUBJECT'S AGE. THE AGE CONCORDANT PARTNER MUST BE AT LEAST FIFTEEN YEARS OLD.
- INDEX PARTNER MUST BE SEXUALLY ACTIVE (ANY ACTIVITY THAT COULD LEAD TO ORGASM)
- CURRENTLY SEEING SOMEONE, DATING, EXPERIMENTING WITH RELATIONSHIPS OR IN A RELATIONSHIP
- HAVE HAD SEX, HOOKED UP WITH OR MADE OUT WITH THAT PERSON
- Both relationship partners must agree to attend an assessment together at an ATN affiliated clinic
- Both partners must be able to communicate in English.
- GENDER IDENTITY AS MALE OR nonbinary, GENDERQUEER, agender OR GENDER NONCONFORMING •MALE SEX AT BIRTH REMOVED ON 8.21.18
- "HAVE THAT PERSON'S AGE BE OVER 14 BUT WITHIN 2 YEARS OF INDEX PARTNER"; ALL PREVIOUS APPROVED CRITERIA STILL APPLY EXCEPT FOR THE AFORMENTIONED DELETED CRITERIA
- To participate in the intervention remotely, youth must be at least 17 and over the age of sexual consent in their state of residence. If participating as a couple, both must be over the age of sexual consent in their state. If a participant lives in the following states and want to participate remotely, they will need to be 18 years old: Arizona, California, Delaware, Florida, Idaho, North Dakota, Oregon, Tennessee, Utah, Virginia, and Wisconsin.

Exclusion Criteria:

YMSM couples will be excluded from the study if they indicate any of the following:

- Unstable, serious psychiatric symptoms
- Current suicidal/homicidal ideation
- Current or prior Intimate Partner Violence (IPV) on the part of either relationship partner
- IF EITHER PARTICIPATING PARTNER FELT PRESSURED OR COERCED TO PARTICIPATE IN THE STUDY OR FELT ANYONE MADE THEM FEEL THEY HAD TO PARTICIPATE IN THEY STUDY WHEN THEY DID NOT WANT TO.

We will include individuals who are not yet adults:

Study procedures involve no more than minimal risk. The nature and scope of the proposed research study, communication skills training and the CHTC intervention do not pose more than "minimal risk" to participants as defined in 45 CFR Part 46.102, "the probability and magnitude of harm or discomfort anticipated in the research are not greater in and of themselves than those

PROTOCOL TITLE:

ordinarily encountered in daily life or during the performance of routine physical or psychological examinations or tests".

We will not include individuals who are adults unable to consent, pregnant women, and prisoners.

11.0 Vulnerable Populations*

We will enroll research participants 15-24 years of age. The nature and scope of the proposed research study and We Test intervention do not pose more than "minimal risk" to participants, as defined in 45CFR Part 46, 102. "the probability and magnitude of harm or discomfort anticipated in the research are not greater in and of themselves than those ordinarily encountered in daily life or during the performance of routine physical or psychological examinations or tests." Given that some participants will be under the age of 18, adequate provisions will be made for soliciting informed consent.

We will not require parental consent for study enrollment. Parental consent may decrease participation rates because some youth will fear that they may be "outed" as a result of participation. Disclosure of sexual orientation may place participating youth at risk for parental harassment, abuse or expulsion from the home.

The intervention and measures utilized in this study are standard in this population, as are waivers of parental permission for survey and interview studies. Additionally, consistent with national policy recommendations from the Society for Adolescent Medicine, requiring parental permission for the proposed study would have a number of possible negative effects, including: (1) reducing the validity of the findings by effectively eliminating potential participants unwilling to share permission forms with their parents/guardians; (2) increasing risk to some youth whose parents have a negative response to the material in the permission forms that would suggest their child has a minority or alternative sexual orientation; and (3) adding little in the way of actual subject protection, given the minimal risk of study participation. Our procedures for the waiver of parental consent are consistent with the guidelines provided by the Department of Health and Human Services: <http://www.hhs.gov/ohrp/humansubjects/guidance/45cfr46.html#subpartd>.

We will obtain assent from participants who are under 18 years of age.

We are protecting this vulnerable by limiting at home testing option to those who meet criteria for FDA approval for Oraquick home testing (17 years of age) and age of sexual consent in their respective state (17 in New York and Michigan, 18 in California).

12.0 Local Number of Subjects

Phase 2: 36 Couples or 72 individuals

Phase 3: 200 individuals

13.0 Recruitment Methods

Recruitment and Screening: Leveraging existing ATN infrastructure, participants will be recruited and screened for eligibility via 2 different ATN sites in Phase 2 and 3 ATN sites in Phase 3 that provide HIV testing and prevention services to YMSM. All ATN clinics, as well as PRIDE, have extensive relations with the gay, lesbian, bisexual, and transgender communities, community service organizations, health service organizations, and providers for MSM. This may be supplemented by online advertising conducted through SIU's Recruitment and Enrollment Core (REC). Potential Participants may be identified at these local sites through testing services, outreach activities, and online social media and dating apps (e.g., Facebook, Instagram, Reddit, Tumbler, Grindr, Scruff, Adam4Adam, Jack'd). While advertising will be distributed through SIU's REC, they will be targeted to the geographic areas surrounding the ATN sites for this project and

PROTOCOL TITLE:

will contain information about participation at the ATN clinic. Given the shift to remote testing, intervention delivery, and study visits in Phase 3 due to COVID-19, recruitment via online advertisements will be expanded nationwide. Couples will be screened through an indexcase approach. One partner in the couple will be asked to provide screening information about themselves and their partner. If the couple is preliminarily eligible based upon the report of the index partner being screened, that index partner will be asked to schedule a baseline appointment. SCHEDULING WILL TAKE PLACE VIA EMAIL, TEXT MESSAGE, AND PHONE at a time both they and their partner can attend. Contact information for the index partner will be collected at this point and added in REDCap for tracking purposes.

Additionally, PRIDE (formerly CHEST) at Hunter College will assist in referring potentially eligible participants to the We Test study through existing online recruitment efforts. PRIDE utilizes the Hunter College IRB-approved Online Master Screener (OMS) to preliminarily screen individuals who are interested in participating in studies being conducted through PRIDE. If an individual is preliminarily eligible for a study, the individual is asked to provide contact information to PRIDE for follow up. For the purposes of this study, the OMS will only be used to refer potentially eligible YMSM to HIV testing sites by sending them an email referral informing them about the We Test study and where to go to determine eligibility after completing the OMS. The contact information collected through the OMS will not be provided to the HIV testing clinic sites. However, We Test clinic sites will be made aware that a potentially eligible YMSM has been referred to their testing services for the study. The OMS, in this instance, will primarily be used as a referral mechanism for the study, directing participants to which study they may be eligible for, including We Test. YMSM who complete the OMS and screen preliminarily eligible, WILL BE CALLED FOR PHONE SCREENING TO DETERMINE STUDY ELIGIBILITY OR SENT A LINK VIA TEXT AND EMAIL. IF THEY ARE ELIGIBLE, THEY WILL BE REFERRED TO THE ATN CLINIC STAFF FOR THE BASELINE APPT.

CHWs who conduct standard of care HIV testing services for the We Test clinic sites will be trained to provide information about the We Test study after HIV-negative results are delivered at their clinic or in the field at mobile testing events. The CHW will be trained in appropriate and ethical methods of recruiting participants in clinical settings and in the field. To minimize the risk for coercion, the staff member and the study information will emphasize the optional nature of participation and that it will not affect, in any way, their access to healthcare services. If the potential participant is interested in finding out if they are eligible for We Test after learning about the study, the CHW will provide an iPad with a secure online REDCap We Test Study Screener (IRB approved). The confidential We Test Study Screener will be completed on the iPad by the potential participant and no one will be able to see the responses; the iPad will only indicate whether the potential participant is eligible. THE WE TEST SCREENER WILL ALSO BE AVAILABLE FOR DELIVERY OVER THE PHONE WITH POTENTIAL PARTICIPANTS BY PRIDE STAFF OR CAN BE COMPLETED AT HOME VIA AN ONLINE LINK.

YMSM who screen ineligible for the study do not need to provide contact information and may screen again after 30 or more days provided they get tested HIV-negative at the clinic site in the past 90 days or they again test HIV-negative at the clinic site. Participants are also able to re-screen should they test HIV-negative at the clinic site or through mobile testing efforts associated with the clinic site.

14.0 Withdrawal of Subjects*

Criteria for Premature Discontinuation

PROTOCOL TITLE:

On the next page, there are the categories of “dropping” participants along with their definitions. These categories should be accurately used in the site’s tracking materials if one of the conditions below occurs.

Category: Definition	Procedure	Notes
Refused baseline (BL) (Prior to Consent): Screened eligible, but never shows up for assessment and/or no longer wishes to be contacted.	Remove from rescheduling call lists and mark as “Do Not Contact” in REDCap.	Counted towards screened number only.
Withdrew during BL (After Consent): Provided consent but refused to finish BL assessment.	Mark as “Baseline concluded” but not “Baseline completed”	Counted up to and including magic number; these participants get marked as “Withdrew from Study” for IRB purposes.
Withdrew during BL (After Consent): Provided consent but their partner refused to participate.	Mark as “Baseline concluded” but not “Baseline completed”	Counted up to and including magic number; these participants get marked as “Withdrew from Study” for IRB purposes.
Withdrew after BL (After Consent): Participant completed the BL but asked to be removed from the study thereafter.	Remove from Follow-Up Call Lists; should be Tracked as enrolled and have a condition assigned.	Counted up to and including randomized/enrolled and stays in all denominators for Follow-Up retention; these participants get marked as “Withdrew from Study” for IRB purposes.
Ineligible during BL (After Consent): Provided consent but was found to be Ineligible during the BL assessment.	Mark as “Baseline concluded” but not “Baseline completed”	Counted up to and including magic number; these participants get marked as “Withdrew from Study” for IRB purposes.
Ineligible after BL (After Consent): Participant either completed the BL, both BL and sessions, OR all BL, sessions and follow-ups but was found ineligible for enrollment at a later date (e.g., found to have psychiatric conditions while collecting BL data)	Remove from Follow-Up Call Lists; should be Tracked as enrolled and have a condition assigned	Counted up to and including randomized/enrolled and stays in all denominators for Follow-Up retention; these participants get marked as “Withdrew from Study” for IRB purposes.
Refused intervention (if applicable), Still Enrolled: Participants who are no longer interested in the	Remain in Database to be called for Follow-Up visits	Treated as other enrolled participants except they wouldn’t show up on session-specific call lists.

PROTOCOL TITLE:

intervention sessions, but have indicated a willingness to continue to be followed for Follow-Up Visits		
Passed away: Participant was enrolled but later passed away	Notify Clinical Site Management Center (CSMC) immediately with details regarding the situation (i.e. Date of Death, Date Notified, Cause of Death, Participant Age and Sex); Remove from Follow-Up Call Lists	Counted up to and including randomized/enrolled and stays in all denominators for Follow-Up retention; these participants get marked as “Withdrew from Study” for IRB purposes.
Other	If a participant withdraws for any other reason not listed here, please contact the CSMC immediately to discuss how to proceed.	

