Aim 2: Test a sustainable model of CHTC implementation in real world adolescent HIV clinics. In line with the implementation science focus of SIU U19, we utilize the EPIS to guide our implementation strategy. We will work with SIU Analytic Core's (AC) health-economist, [name], to conduct cost-effectiveness analyses to inform implementation decision-making. In collaboration with SIU ISC, we will document provider feedback to training and intervention materials to modify materials and create training packages for broad dissemination.

We will achieve our aims over two phases of the study.

PROTOCOL TITLE:

Phase 2 (n=36 couples): involves a pilot randomized control trial (RCT) to evaluate the acceptability, feasibility, and preliminary efficacy of these adjunct components.

Phase 3 (n=200 individuals): involves a CET comparing the most promising intervention package from Phase 2, consisting of individual MI, ACT video+ a recognition survey, and CHTC, compared to individual HIV testing and counseling (IHTC) delivered as usual. Participants in either condition can come as an individual or with their partner or come first as an individual and then bring their partner. This phase is focused on Implementation and Sustainment phases of the EPIS model informed by outcome analyses, cost analyses, and feedback from youth and ATN staff.

Phase 3 has now been added to this protocol document.

Hypothesis: The primary hypothesis is that because of developing skills in self-management and assertive communication, inclusion of adjunct components will be associated with clinically significant decreases in HIV transmission risk behavior as compared with partnered YMSM who receive individual testing and counseling (only). Secondarily, we propose that these intervention effects will be mediated by assertive communication skills.

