6.0 Procedures Involved*

Enrollment and Consent: Utilizing enrollment procedures established within ATN, clinic staff will invite YMSM who present for HIV testing services the opportunity to screen. These interested index partners will complete a brief iPad eligibility screener.

For Phase 2, IF ELIGIBLE, THE SCREENER WILL RANDOMIZE THEM TO COMPLETE THE BASELINE AS A COUPLE OR AN INDIVIDUAL.

If randomized to individual, staff will schedule a baseline assessment for the invited youth. If randomized to couple, staff will schedule a baseline assessment for the invited youth at a time both they and their relationship/romantic partner are available. Partners

PROTOCOL TITLE:

will independently complete informed consent at the beginning of the baseline visit, prior to assessment following ATN-wide established protocols.

FOR PHASE 2, IF THE YOUTH IS RANDOMIZED TO COMPLETE THE BASELINE AS A COUPLE, AND THEY INDICATE THAT THEY WILL BE UNABLE TO HAVE THEIR PARTNER COME FOR THE APPOINTMENT, THEY WILL BE ALLOWED TO COME TO THE BASELINE AS AN INDIVIDUAL.

For Phase 3, study sites are given the options to deliver the intervention in-person as usual, or entirely remote delivery. This is to allow sites more flexibility surrounding COVID-19 closures and restrictions, which vary by site.

For Phase 3, index partners will be able to choose to attend their baseline appointment on their own or with their partner. While scheduling the baseline, staff will ascertain whether the participant is planning to come in alone or with their partner so they can reserve adequate time, space and resources for the appointment. Regardless of whether the index partner attends alone or with their partner, after the participant(s) complete the survey at the beginning of the baseline appointment, the index partner will be randomized to the We Test intervention or individual HIV testing (IHTC) as usual. If alone and randomized to the We Test intervention, the index partner will participate in the intervention as an individual. If both members of the couple attend and are randomized to We Test, they will participate in the intervention as a couple. If both members of the couple attend and are randomized to IHTC, they will each receive IHTC as usual. The index partner who participates as an individual (in either condition) will be offered the opportunity to bring their partner to participate in the WeTest. The partner will be enrolled into the same condition as the index partner.

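### Randomised participants found ineligible after baseline are taken off the follow-up lists, so outcomes go uncollected on grounds that could, but are not shown to, be detected unequally by arm

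*Protocol*

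**What the plan says.** The withdrawal table in Protocol 14.0 has a row for a participant who got through the baseline visit but "was found ineligible for enrollment at a later date". It covers people who finished the baseline only, the baseline and sessions, or everything including follow-ups. The procedure is "Remove from Follow-Up Call Lists; should be Tracked as enrolled and have a condition assigned". The counting note reads "Counted up to and including randomized/enrolled and stays in all denominators for Follow-Up retention", and the same note has them marked as withdrawn for IRB purposes. The one example of late ineligibility is "found to have psychiatric conditions while collecting BL data".

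A later row of the same table treats participants who refuse the intervention differently: they stay in the database and are called for follow-up visits.

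On timing, Protocol 6.0 says that in Phase 3 "after the participant(s) complete the survey at the beginning of the baseline appointment, the index partner will be randomized to the We Test intervention" or to usual individual testing; HIV and STI testing and Session 1 come after that. Protocol 2.0 describes the Phase 3 intervention as "consisting of individual MI, ACT video+ a recognition survey, and CHTC, compared to individual HIV testing and counseling (IHTC) delivered as usual". The exclusions in Protocol 10.0 include "Current or prior Intimate Partner Violence (IPV) on the part of either relationship partner" and "Unstable, serious psychiatric symptoms", together with current suicidal or homicidal ideation and feeling coerced to take part.

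The SAP names no analysis population and does not mention this group. Its attrition analysis (section headed Equivalency Tests) compares retained and lost participants on demographics and baseline outcomes; condition is not listed. It offers full-information maximum likelihood, with models for non-random missingness to be explored where indicated.

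**The concern.** Eligibility is a pre-randomisation matter. Once a person has been allocated, a later finding of ineligibility is no reason in itself to stop measuring the outcome. The rule stops it anyway, for people who have not withdrawn, and gives no reason. Remaining in the retention denominator is bookkeeping and recovers no data.

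Two things are at stake. The first is avoidable missing data. This can reach beyond the person removed, because two of the four risk outcomes in SAP 1.2 depend on the primary partner's report or STI result. The second is possible selection. If the grounds for removal come to light more often in one arm, and those removed differ in sexual risk, the arms being compared are no longer the arms that were randomised. A likelihood analysis that assumes data are missing at random would not fully correct that.

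**Working it through.** **Does the rule stop outcome collection?** Setting the rows of Protocol 14.0 side by side:

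- Refused the intervention: still called for follow-up.
- Withdrew after baseline, or died: removed from the lists, unavoidably.
- Found ineligible after baseline: removed from the lists, although the participant has neither withdrawn nor refused.

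Only the last is a choice of the plan. Anyone in that row who had already completed every follow-up loses no data, though the SAP does not say whether those data are analysed.

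**How large could a bias be?** The documents give no figure for late ineligibility, so there is nothing to reproduce, and every input below is an assumption. Let s be the share truly ineligible (the same in both arms), p_e and p_i the outcome rates among eligible and ineligible participants, and d the share of the ineligible who are detected and removed in an arm. Assume that those removed contribute no outcome, that the true effect is nil, and that there are 100 per arm (the protocol's 200 individuals, equal allocation assumed). Then

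observed rate = [(1 − s)·p_e + s(1 − d)·p_i] / (1 − s·d).

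With p_e = 0.30:

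| s | d, IHTC / We Test | p_i | Removed per 100, IHTC / We Test | Observed rate, IHTC / We Test | Difference (points) | OR |
|---|---|---|---|---|---|---|
| 5% | 0% / 50% | 45% | 0 / 2.5 | 0.3075 / 0.3038 | −0.4 | 0.98 |
| 5% | 20% / 80% | 60% | 1 / 4 | 0.3121 / 0.3031 | −0.9 | 0.96 |
| 10% | 20% / 80% | 60% | 2 / 8 | 0.3245 / 0.3065 | −1.8 | 0.92 |
| 10% | 0% / 100% | 60% | 0 / 10 | 0.3300 / 0.3000 | −3.0 | 0.87 |
| 10% | 50% / 50% | 60% | 5 / 5 | 0.3158 / 0.3158 | 0.0 | 1.00 |

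Fourth row worked through: IHTC = 0.90 × 0.30 + 0.10 × 0.60 = 0.33; We Test = (0.90 × 0.30) / 0.90 = 0.30; OR = (0.30/0.70) / (0.33/0.67) = 0.87.

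A second parametrisation agrees. Take a 30% rate overall and 50% among those removed, so the observed rate is (0.30 − 0.50d)/(1 − d), where d is now the share of the whole arm removed. Removing 5% against 1% gives 0.275/0.95 = 0.289 against 0.295/0.99 = 0.298, OR 0.96. Removing 10% against 2% gives 0.278 against 0.296, OR 0.92.

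**Which way does it go?** The observed rate can be written p_e + w(p_i − p_e), with w = s(1 − d)/(1 − s·d). The difference between arms is therefore (w for We Test − w for IHTC) × (p_i − p_e). It is zero if detection is equal, or if those removed carry the same risk as the rest. It reverses if they carry lower risk, or if IHTC detects more.

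**What about power?** The SAP expects 232 of 288 retained (80.6%). Applied to 200 individuals, that leaves 200 × 232/288 = 161, or about 80 per arm. Take the SAP's odds ratio of 0.44 (a 56% reduction in odds) and an assumed 30% control rate, two-sided 5%. A simple two-proportion calculation that ignores clustering and repeated measures then gives power of 0.57. Losing five more per arm gives 0.54. This gauges the change only; it does not reproduce the SAP's simulation.

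**The case against.** The strongest reply concerns arm-dependence. A reader might infer that We Test, with its motivational interview and couples counselling, will uncover more partner violence or distress than usual testing, and that the resulting bias favours the intervention. The documents do not support going that far:

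- No section says that late ineligibility is found more often in one arm.
- The rule's only example is a finding from baseline data, and in Phase 3 the baseline survey is completed before allocation.
- Screening comes before the baseline visit, and consent is taken privately to limit partner pressure.
- Follow-up surveys and tests are the same in both arms.
- No session length is given. We Test participants who attend alone receive the intervention as individuals, and usual testing also includes counselling.
- A stated direction needs a second assumption, that those removed are at higher risk, for which there is no evidence in the documents.

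A reader might also conclude that intention-to-treat is breached. That is too strong. These participants stay enrolled in their assigned condition, nothing excludes the data already collected, and the growth model can use the waves they completed. The accurate statement is that follow-up is incomplete and the analysis population is not stated.

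The SAP's missing-data text deserves credit as well: it allows for modelling non-random missingness. But that is optional, depends on untestable assumptions, and does not recover outcomes that could simply have been collected.

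What stands is the rule itself. It stops follow-up after randomisation in people who did not withdraw. The category expressly includes people who have had sessions, the arms differ in session content, and the documents do not say whether the person judging eligibility is unaware of the arm. Unequal detection is therefore possible.

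**Conclusion.** The point holds as a cheap improvement. It is certain that the rule leaves outcomes uncollected for randomised participants who did not ask to leave, and that neither document offsets this. It is possible, but not shown, that the loss differs by arm. Any bias is likely to be small and its direction is not established: an odds ratio of about 0.98 to 0.87 under a true null if We Test detects more and those removed are at higher risk, and 1.00 if detection is equal. These figures rest wholly on assumed detection shares, assumed outcome rates and 5–10% true ineligibility. The planning effects in the SAP (odds ratios of 0.44 and 0.17) are much larger, and the cost in power is slight. The case for changing the rule is that the loss is avoidable, not that a harmful bias has been demonstrated.

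**What to change.** Reword the row in Protocol 14.0 so that randomised participants found ineligible later stay on the follow-up lists for the CASI and for HIV and STI testing. Allow three exceptions: they withdraw, their consent is in doubt (for example, they report having been coerced), or a documented safety reason prevents contact. Bring the withdrawn-from-study marking into line, since continued contact is inconsistent with that status.

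In the SAP, state that these participants are analysed in the assigned arm. Any exclusion from an analysis should rest only on pre-randomisation information, judged without knowledge of the arm. Report the number found ineligible late, and the reason, by arm.

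The cost is a few extra follow-up contacts and a small change to the tracking and IRB-status wording. For participants who remain in follow-up, it removes the loss that this rule creates; what is left is confined to the three exceptions and becomes visible in the report by arm.
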